#### Exclusion criteria

- 1. Active tuberculosis or untreated latent tuberculosis (e.g., positive interferon-γ release assay [IGRA] test, such as Quantiferon-gold)
- 2. Untreated active hepatitis B or C infection Active hepatitis B is defined as positive surface antigen; active hepatitis C is defined as positive antibody and positive polymerase chain reaction (PCR)
- 3. Any of the following baseline lab values
  - a. White blood count <3500 cells per microliter
  - b. Platelets <100,000 per microliter
  - c. Hematocrit <30%
  - d. AST or ALT >1.5X upper limit normal value
  - e. Serum creatinine >1.1X upper limit normal value
- 4. Behçet disease
- 5. Multiple sclerosis or other demyelinating disease
- 6. For patients with anterior/intermediate or intermediate uveitis without systemic disease, abnormal magnetic resonance imaging (MRI) of the brain consistent with demyelinating disease
- 7. Severe uncontrolled infection
- 8. Receipt of a live vaccine within past 30 days

- 9. Moderate to severe heart failure (NYHA class III/IV)
- 10. Active malignancy
- 11. Use of anti-TNF monoclonal antibody therapy within past 60 days
- 12. History of adalimumab intolerance or ineffectiveness
- 13. Hypersensitivity to any of the study treatments or their excipients
- 14. Current treatment with an alkylating agent
- 15. Current treatment with more than one immunosuppressive drug, not including oral corticosteroids
- 16. Shorter-acting regional corticosteroids administered within the past 30 days in any eye(s) with uveitis
- 17. Long-acting ocular corticosteroid implants, i.e., fluocinolone acetonide implant (e.g., Retisert®, Yutiq™, Iluvien®) placed within past 3 years unless uveitis is active in all eye(s) with an implant
- 18. Systemic disease that is sufficiently active such that it dictates therapy with systemic corticosteroids or immunosuppressive agents at the time of enrollment
- 19. Immunodeficiency disease for which immunosuppressive therapy would be contraindicated according to best medical judgment
- 20. Pregnancy or lactation
- 21. For persons of child-bearing potential or impregnating potential, unwillingness to use appropriate birth control (abstinence, combination barrier and spermicide, hormonal, or intrauterine device) for the next 18 months or plans to become a biological parent within the next 18 months.
  - \* In the UK, use of combination barrier and spermicide alone does not meet birth control requirements.

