# Management of conventional immunosuppressive agents for patients who are on one at baseline

Patients in the adalimumab treatment group who already are taking a conventional immunosuppressive drug will continue that drug throughout the study (in addition to the adalimumab) unless some contraindication to continuation arises. Those for whom existing immunosuppressive therapy is deemed non-useful should discontinue it before entering the study.

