#### 4.6 Monitoring for toxicity of immunosuppressive drugs

Patients will be monitored for potential toxicities of adalimumab or conventional immunosuppressive therapy/therapies using the schedule described in the Trial's follow-up schedule (Table 2), i.e., complete blood count and chemistry panel including creatinine and liver enzymes will be conducted at every study visit and monitoring and prevention strategies will be implemented as detailed in Table 7. Potential Risks of Therapy. As applicable, additional monitoring studies should be carried out per routine care. When potential toxicities are encountered, modification of therapy, including dose reduction or discontinuation as clinically appropriate, should be done along the lines indicated in published guidelines.

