*Infection:* even without an increased risk of leukopenia among patients in the (unmasked) MUST Trial on systemic therapy, there was an increased use of antibiotics for infection. However, there were no long-term sequelae from these infections, and no increase in the risk of hospitalization for infection. Patients will be queried about infections at every visit, and medical records reviewed as necessary, to monitor for infections. Hospitalization data also will be collected. In non-uveitis use (e.g., transplants) some immunosuppressive regimens may increase the risk of severe opportunistic infections (e.g., progressive multifocal leukoencephalopathy), which can have serious consequences, including death. Although there were no such events in the MUST Trial, because of their rare nature, their possible occurrence in the ADVISE Trial or routine clinical practice using these drugs cannot be excluded.

Additional recognized potential complications of potent immunosuppressive therapy will be deemed to be present when diagnosis is confirmed by medical records. These conditions specifically will include a diagnosis of any of the following conditions (if not present at baseline): a) liver cirrhosis; b) interstitial pneumonitis; c) possibly malignancy (drug-specific); d) end-stage renal insufficiency.

In addition to these small molecule immunosuppressive agents, the anti-TNF-α biologic agent adalimumab will be used. The most common adverse reaction of adalimumab is redness, itching, pain, or swelling at the injection site, reported in 20% of patients. Other less common adverse events include: increased risk of infections, particularly tuberculosis, fungal infections, and herpes zoster. Patents randomized to adalimumab will be instructed not to get any live

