vaccines. Other uncommon potential adverse effects include gastrointestinal symptoms such as nausea, vomiting, abdominal pain, or diarrhea; reversible bone marrow suppression; and reversible hepatotoxicity. Other rare adverse events include: development of anti-adalimumab antibodies and a lupus erythematosus-like syndrome, and a worsening of demyelinating disease, such as multiple sclerosis. All patients enrolled in the ADVISE Trial will have tuberculosis testing with either an interferon-γ release assay test, such as the Quantiferon-gold test and testing for active hepatitis B or C infection prior to enrollment. Active tuberculosis and untreated latent tuberculosis and untreated active hepatitis B or C infection are exclusions to participation. Because of the increased risk of multiple sclerosis in patients with pars planitis and undifferentiated intermediate uveitis, all potential participants with these two diseases will undergo neuro-imaging with a gadolinium enhanced MRI scan and patients with evidence of possible demyelination are excluded from the trial.

Use of the following medications are prohibited during the trial for safety reasons

- Live vaccines
- Substrates for the multidrug efflux transporter P-glycoprotein or the organic anion transporter proteins (OATP) and for which elevated plasma concentrations are associated with serious and/or life threatening events, e.g. bosentan, dabigatran etexilate and aliskiren.
- Products containing Hypericum perforatum (St John's Wort) to avoid risk of interaction with tacrolimus that lead to either a decrease in blood concentrations of tacrolimus and reduced clinical effect of tacrolimus, or an increase in blood concentrations of tacrolimus and risk of tacrolimus

Treatment	Group affected	Systemic	Monitoring & Prevention Strategy
Corticosteroids	Both groups	Hyperglycemia	History; CMP testing
		Hypertension	History; BP measurement
		Osteoporosis	Routine monitoring/ data collection
		Hyperlipidemia	Routine monitoring/ data collection
		Infection	Routine monitoring/ data collection
		Cardiovascular Disease	Routine monitoring/ data collection; Monitor risk factors (per above)
		Cataract	Slit lamp examination/Eye Exam
		Intraocular Pressure Elevation and Glaucoma	Eye Examination
Adalimumab	Adalimumab	Infection	Pre-randomization tuberculosis and hepatitis B and C testing; Routine monitoring/ data collection. Live vaccines should not be given.

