		Worsening of multiple sclerosis	MRI of patients with intermediate uveitis at BL; Routine monitoring/ data collection
		Injection Site Reaction*	Routine monitoring/ data collection
		Bone marrow toxicity*	CBC testing
		Hepatotoxicity*	CMP testing, pre-treatment Hepatitis panel
Methotrexate	Conventional	Bone marrow toxicity*	CBC testing
		Hepatotoxicity*	CMP testing, pre-treatment Hepatitis panel
		GI intolerance*	History/Routine monitoring
		Teratogenicity/ Miscarriage	Birth control use for women and men
		Alopecia*	Routine monitoring/ data collection
Mycophenolate	Conventional	Bone marrow toxicity*	CBC testing
		Hepatotoxicity*	CMP testing, pre-treatment Hepatitis panel
		GI intolerance*	History/Routine monitoring
		Teratogenicity	Birth control use
		Possibly PML (disputed)	History/Routine monitoring

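### The live-vaccine instruction in protocol section 6 is narrower than that section's own prohibition, and Table 7 assigns conventional drugs to one arm although both arms can take them

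*Protocol*

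**What the plan says.** **Live vaccines.** Four places in the protocol bear on this.

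- The section 6 paragraph on adalimumab's adverse effects states "Patents randomized to adalimumab will be instructed not to get any live" vaccines (the sentence ends after a page break).
- In Table 7 (the table of potential risks of therapy), the infection row for adalimumab, with that arm as the group affected, carries the remark "Live vaccines should not be given". No other row mentions live vaccines.
- The last part of section 6 opens a list with "Use of the following medications are prohibited during the trial for safety reasons". Live vaccines are its first item, and no arm is named.
- Section 3.5 excludes any candidate with "Receipt of a live vaccine within past 30 days", again in either arm.

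**Conventional drugs.** Table 7 has a column for the group affected. Corticosteroids are marked as affecting both groups. Methotrexate is entered as "Methotrexate Conventional", and mycophenolate, azathioprine, cyclosporine and tacrolimus carry the same label. Section 4.6 gives the table force: "monitoring and prevention strategies will be implemented as detailed in Table 7".

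The treatment rules put those same drugs in the adalimumab arm. Section 4.3.1 states: "Patients in the adalimumab treatment group who already are taking a conventional immunosuppressive drug will continue that drug throughout the study". Section 4.4 allows an adalimumab patient one conventional drug when treatment is advanced. Table 6b directs that one be added for a patient on adalimumab alone whose uveitis reactivates; an antimetabolite is preferred, but either class is acceptable.

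**The concern.** A prohibition on vaccines depends largely on the patient knowing about it, since vaccines are often given outside the study clinic. If the only instruction written into the protocol is addressed to one arm while the prohibition covers both, two sites can read section 6 differently and each point to a sentence in support.

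The Table 7 label raises a similar problem. Because the corticosteroid rows are marked for both groups, the column evidently refers to randomized arms, so an entry naming one arm reads as leaving out the other. For the five conventional drugs that contradicts sections 4.3.1 and 4.4 and Table 6b. A site that used the column to decide which rows apply to a patient would not be pointed to the second drug of an adalimumab patient on combination treatment.

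**Working it through.** No power or error-rate figure is involved. The check sets the passages side by side and counts the patients concerned.

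**1. Population named by each live-vaccine statement**

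| Place | Population |
|---|---|
| Section 6, adalimumab paragraph | Adalimumab arm |
| Table 7, adalimumab infection row | Adalimumab arm |
| Section 6, closing list | All participants, during the trial |
| Section 3.5, exclusion | All candidates, the 30 days before entry |

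Section 3.1 gives 222 patients, 111 per arm. Covered by the prohibition: 222. Covered by the written instruction: 111. Difference: 222 − 111 = 111, the conventional arm. The entry exclusion does not close this difference, because it looks backwards from enrollment.

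The revision history for version 1.2 records the prohibited list as an addition and says that the St John's Wort item was also entered in Table 7. It mentions no matching Table 7 change for live vaccines. Incomplete carry-over would explain the mismatch, but this is an inference.

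**2. Adalimumab patients taking a drug that Table 7 assigns to the other arm**

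Inputs: 111 patients in the arm (section 3.1) and 25% expected to be on one agent at enrollment (section 8.2 and SAP section 6.2). Randomization is stratified on this factor, so the same share should hold approximately within the arm.

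- On a conventional drug from baseline: 0.25 × 111 = 27.75, about 28.
- Drug added during follow-up (section 4.4, Table 6b): the documents give no figure, so none is computed.

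Since Table 6b accepts either class, any of the five drugs could be taken in the adalimumab arm.

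**3. What reaches both arms regardless of the label**

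| Table 7 item | Provision elsewhere | Applies to |
|---|---|---|
| Marrow, liver, kidney, glucose | Blood count and chemistry at every visit (3.7, 4.6) | All |
| Hypertension | Blood pressure at every visit (3.7) | All |
| GI intolerance, tremor, alopecia, hirsutism, gingival hyperplasia | Medical and treatment history at every visit (3.7) | All |
| Teratogenicity | Contraception criterion (3.5); advice in section 6; pregnancy stopping (4.7.2) | All, or by drug taken |
| Tacrolimus and St John's Wort | Closing list of section 6 | All |

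For these items the label error costs little or no protection. What remains is that the table does not point sites to the adalimumab patients for whom the history-based rows are relevant.

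**The case against.** The strongest reply is that nothing here permits a live vaccine in the conventional arm. The section 6 sentence stands in a paragraph on adalimumab's own adverse effects and does not say that only that arm is to be instructed. The prohibition later in the same section is plain and unrestricted. That is correct. A reader might infer from the sentence that live vaccines are to be avoided in one arm only, and the documents do not support that reading.

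A reader might also infer that conventional-arm patients are never told of the prohibition. That cannot be established. Consent pages are not part of the material reviewed and the Manual of Procedures was not supplied, so either may contain the instruction. The finding is confined to what the protocol itself says.

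On Table 7, the reply is that its rows are organised by drug, that the section 6 narrative describes toxicities by drug, and that a site would hardly disregard the methotrexate row for a patient taking methotrexate. Most of this stands too. Section 6 as a whole does not tie precautions to the randomized arm, and the provisions in step 3 of the working cover nearly every row. It does not make the column correct: the label conflicts with the treatment rules, and section 4.6 tells sites to follow that table.

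**Conclusion.** Both inconsistencies are real, and the text is wrong as written. The severity is minor.

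On live vaccines, the instruction and the Table 7 entry cover 111 patients and the prohibition covers 222. On the conventional drugs, the column is incorrect for about 28 of 111 adalimumab patients (25%) from baseline, provided the protocol's planning share holds in that arm, and for an unstated number later.

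A reader might extend the second count by assuming that the planned 25% without success among the other 83 adalimumab patients all have a drug added: 0.25 × 83 ≈ 21, giving 28 + 21 = 49 of 111 (44%). The documents do not support this as an estimate or as an upper limit. A drug is added for lack of control four weeks after starting study treatment or for reactivation, not for failure at six months, and a patient who has one added may still succeed.

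Nor do these counts measure lost protection, since scheduled monitoring and most preventive measures already reach both arms. The main gain from correction is one unambiguous statement on live vaccines.

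**What to change.** Reconcile the section 6 sentence, the Table 7 adalimumab entry and the closing list so that all three state the same population for live vaccines. Which population that is, and the clinical content, are for the sponsor to decide.

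In Table 7, make the group-affected entries for the five conventional drugs agree with sections 4.3.1 and 4.4 and Table 6b by defining them by drug received, in either arm.

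Check the Manual of Procedures, site instructions and prototype consent against the result and amend them where they differ.

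The cost is one sentence, one table entry and one column of labels, plus matching text elsewhere if needed. No visit, test, sample size or analysis changes.

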# Table 8. Potential risks of therapy

Treatment	Group affected	Systemic	Monitoring & Prevention Strategy
Azathioprine	Conventional	Bone marrow toxicity*	CBC testing
		Hepatotoxicity*	CMP testing, pre-treatment Hepatitis panel
		GI intolerance*	History/Routine monitoring
Cyclosporine	Conventional	Hypertension*	History; BP measurement
		Renal insufficiency*	CMP testing
		Tremor/paresthesia*	History/Routine monitoring
		Hirsutism*	History/Routine monitoring
		Gingival hyperplasia*	History/Routine monitoring
Tacrolimus	Conventional	Hypertension*	History; BP measurement
		Renal insufficiency*	CMP testing
		Tremor/paresthesia*	History/Routine monitoring
		Hyperglycemia*	History; CMP testing
		Interactions with products containing Hypericum perforatum	Products containing Hypericum perforatum (St John´s Wort).may not used during the study

\*Usually reversible with dose adjustment or cessation of therapy

CMP=complete metabolic panel; BP=blood pressure; CBC=complete blood count

# 7. Safety reporting of adverse events

# 7.1 Adverse events

Adverse events (AEs) and complications of study treatment will be submitted to the CC. As described in section 7.2, all serious adverse events (SAEs) will require expedited reporting to the CC for immediate review by the CC Safety Officer who will determine any further actions required including whether the event requires expedited review by the Data and Safety Monitoring Committee (DSMC) Safety Officer. The CC and DSMC Safety Officers will make recommendations to the DSMC as to any actions that may be needed.

### 7.2 Serious adverse events

An SAE is an adverse event that results in one of the following outcomes: death, a lifethreatening adverse drug experience, inpatient hospitalization or prolongation of existing hospitalization, a persistent or significant disability/incapacity, or congenital anomaly/birth defect. Also, important medical events that may not result in death, be life-threatening, or require hospitalization may be considered a serious adverse event when, based upon appropriate medical judgment, they may jeopardize the patient or subject and may require medical or surgical intervention (treatment) to prevent any of the outcomes previously listed in this definition.

Clinical centers will report all SAEs to the CC expeditiously regardless of the relationship to study treatment. When an investigator or clinical center staff member becomes aware of an SAE, it will be reported to the CC within 72 hours (within 24 hours for UK clinics only\*) with follow up reporting until the event is terminated. The SAE report will include an assessment by the clinical investigator at the managing clinical center as to the likelihood whether the event is related to treatment. Upon receipt at the CC, the SAE report will be sent to the CC Safety Officer for immediate review and determination as to whether the event meets the criteria for a safety report and whether expedited review by the DSMC Safety Officer is warranted.

All serious and unexpected events possibly related to study treatment will be reported as safety reports to the NEI project officer, the pharmaceutical supplier (where appropriate), applicable regulatory agencies (.e.g., FDA and Health Canada), and all clinical centers in accordance with applicable regulations. The CC and clinical centers will submit all safety reports as expedited reports to their Institutional Review Boards (IRBs). Reports of SAEs not deemed to be unexpected will be submitted to the CC's IRB, to the IRB of the clinical center in which the event was reported, as well as to any other study center IRBs which require such reports.

\*For compliance with the CT3 directive (2011/C 172/01) (Section 4.3.1): "Communication from the European Commission — Detailed guidance on the collection, verification and presentation of adverse event/reaction reports arising from clinicaltrials on medicinal products for human use

# 8. Sample size and statistical methods

# 8.1 Hypotheses

The primary hypothesis is that adalimumab will be superior to conventional immunosuppression for corticosteroid sparing, as determined by the proportion of participants that achieve the primary outcome, namely inactive uveitis and prednisone  $\leq$ 7.5 mg/day for 2 visits  $\geq$ 28 days apart by 6 months of follow-up. The 6-month time frame was chosen to allow sufficient time to observe the primary outcome regardless of the patient's prednisone dose at randomization and is likely to be more robust to imbalances.

Secondary hypothesis are that adalimumab will be superior to conventional immunosuppression for:

- Corticosteroid sparing (inactive uveitis and prednisone <7.5 mg/day for 2 visits >28 days) apart by one year of follow-up
- Prednisone discontinuation (inactive uveitis for 2 visits >28 days after discontinuation of prednisone) by one year.

Furthermore, we hypothesize that these benefits will be accomplished with no increase in ocular or systemic adverse events (other than injection site reactions) with adalimumab, and that both approaches will produce similarly visual acuity and incidences of uveitic complications.

# 8.2 Sample size and power calculations

Sample size is calculated for the primary comparison of corticosteroid-sparing treatment success (inactive uveitis and prednisone <7.5 mg/day for 2 consecutive visits >28 days apart) at 6 months. Based on the preliminary data from the VISUAL III Study, we estimate that adalimumab will be successful in achieving the primary outcome in 75% of patients across all strata. The success of conventional small molecule immunosuppression varies according to the type and number of treatments. Based upon the Mount Sinai and MUST Trial data, we estimate that 75% of the participants will be in the stratum of no prior immunosuppression and 25% will be on one immunosuppressive agent at enrollment. Based on the SITE data, the estimated success rate for antimetabolites is 55% and for calcineurin inhibitors 40%. Patients in the no immunosuppression stratum will receive antimetabolites, whereas those in the one immunosuppression stratum will largely receive calcineurin inhibitors. Therefore, success rates of 55% and 40% are estimated for the no and one immunosuppressive agent strata. respectively. Based on the estimated stratum proportions and corresponding success rates, the overall conventional immunosuppression success rate is estimated to be 51%. In the MUST Trial, the loss to follow-up was 6% at 2 years. In order to be conservative, we will assume a 10% loss to follow-up in each group and that all individuals were lost prior to observing a result. Under these assumptions, a sample size of 222 (111 participants per treatment group) provides 90% power to detect significant differences between the 2 aroups if the underlying true proportions are 51% vs. 75% (46.1% vs. 67.5%, respectively, after adjusting for the loss to follow-up), assuming a two-sided type I error of 0.05. VISUAL I and II, while not appropriate for estimation of corticosteroid-sparing due to a rapid taper, do provide some estimates of the ability to discontinue prednisone, which can be estimated as 50%. Based upon data from Mount Sinai and the MUST Trial, estimates of the discontinuation rates for standard immunotherapy range between 11%-35%. A sample size of 222 provides 80% power to detect an increase in the secondary outcome of discontinuing prednisone while controlling the uveitis

by 1 year from 30% to 50% (estimated from VISUAL I and II data), assuming a two-sided type I error of 0.05.

